Aim 1b. Using qualitative interviews, self-report instruments, and medical records, we will describe the extent to which community healthcare professionals providing care to pregnant and postpartum women with suicidal ideation report the knowledge base and requisite skills to address suicidal ideation and behavior in the real-world population of healthcare providers serving the sample of women enrolled in Aim 1a (n = 125).

Aim 1c. Using a cross-sectional design, we will describe the characteristics and correlates of suicidal ideation and behavior among pregnant women (n = 550).

Arm 2 (**Aim 2**): Using expanded entry criteria in our parent grant pragmatic trial design, we will explore the safety, feasibility, and acceptability of expanding study entry criteria specifically to enroll pregnant women with any reports of suicidal ideation or behavior (n = 40) in a proof of concept randomized controlled trial of MMB for Moms to enhanced usual care.

III. SUBJECT SELECTION

UPWARD and UPWARD Extension

Inclusion Criteria

- 1) Pregnant women (prior to 16 weeks' gestation)
- 2) Age 18 or older
- 3) History of recurrent major depression prior to pregnancy (at least two prior episodes, one of which may be currently treated)
- 4) Euthymic or with residual symptoms (PHQ9 ≤ 9)
- 5) No depressive relapse since the last menstrual period (LMP)

- 6) Currently or recently receiving antidepressants (at most 12 weeks prior to LMP)
- 7) Presence of an ongoing community prescriber/provider

Exclusion Criteria

- 1) Diagnosis of bipolar or psychotic disorder
- 2) Mania, psychosis, or active substance abuse (within last 6 months for substance abuse)
- 3) Immediate risk of self-harm
- 4) Non-English speaking

Drop Criteria

- 1) Inability or unwillingness to complete study procedures
- 2) Suicide attempt made during the course of the study if they do not have the appropriate psychiatric/behavioral health care in place locally as determined by a study physician. To be considered appropriately cared for, participants must be able to identify at least 1 mental health or prenatal provider by name and have an appointment scheduled with an outpatient provider within 10 days of the attempt.

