Participants in the UPWARD Study and UPWARD-S Arm 2 are randomly assigned to participate in MMB. The 8-session protocol for MMB is based on the theory that proposes that individuals with histories of depression are vulnerable during dysphoric states, during which maladaptive cognitive patterns present during previous episodes are reactivated and can trigger the onset of a new episode.²² Formal and informal mindfulness practice and cognitive behavioral skills are taught to help participants cultivate mindful rather than automatic, depressogenic modes of relating to thoughts, emotions, and sensations. Additions to the standard MBCT curriculum for pregnant women are designed to increase engagement and include brief informal mindfulness, social support, and self-compassion practices as well as psychoeducation about mood and anxiety during the transition to parenthood. Our digital delivery of MBCT, called Mindful Mood Balance for Moms (MMB for Moms; see Table 2), is delivered in a mobile first digital format, which can be accessed fully from desktop or mobile devices. It is provided in an individually tailored manner that replicates the core components of the in-person MBCT program.

Specifically, each session engages a sequential tripartite learning cycle that is core to the in-person MBCT program (Experiential Practice, Video-Based Vicarious Learning, and Didactic Information). This provides patients with the opportunity for threefold presentation of content, but accessed through unique and overlapping receptive learning modes.^{23,24} Accompanying materials are provided for each session via digital access to forms and audio or video guides identical to those used in standard MBCT, but modified for digital delivery (e.g., presented in a more interactive format, shortened to accommodate the typical amount of text presented on screen). Participants are asked to logon to the program on a daily basis until program completion and to set a regular routine for sessions and homework practice. The digital platform

for MMB will be hosted at Brella for the study's duration. Direct access to the server is secured by a firewall with IP whitelisting and account verification. HTTPS, SSL access, and user passwords are secured with 256-bit level encryption.

The MMB for Moms program also includes social community functionality.

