For the analysis of rates of relapse, we will examine time to relapse as rated by the MINI during pregnancy and across the 6-month postpartum follow up using survival analysis. Survival rates will be compared using Cox proportional hazard regression and illustrated in Kaplan-Meier curves (Collett, 1994). However, time to attrition is a competing risk that can be related to time to relapse. We will adopt the subdistribution hazard model (SHM) developed by Fine and Gray to account for the possible non-independence of the censoring mechanism.²⁵

For the continuous outcomes, we will use Hierarchical Linear Models (HLM) as our primary analytic model, which will compare change over time between groups on depressive symptom burden using the PHQ-9. HLM is flexible with respect to the nature of change over time (i.e., linear, piecewise linear, loglinear, etc.), and will accommodate the within subject correlation through the inclusion of random effects at the patient-level, accounting for the patient-to-patient deviations. Pattern-mixture models²⁶ will be used to assess whether important estimates (i.e., intervention effects) are dependent on missing data and to provide overall estimates of effects by averaging over the various missing-data patterns.

Analysis for Specific Aim #2: To explore the specific benefit of MMB relative to AD discontinuation and questions regarding personalization that are of strong interest to pregnant women and their healthcare providers.

H2a: Comparison of MMB to UC among women who discontinue AD: Our analysis will be the same as H1 with both the time-to relapse and continuous outcome models. We predict that rates of relapse and symptom burden among women randomized to MMB who discontinue AD will be significantly superior to those randomized to UC who discontinue AD.

H2b: Treatment Selection Algorithm: We predict that the use of a treatment selection algorithm will differentiate two profiles of women based on pre-treatment characteristics (those who are optimally suited to discontinue AD and engage MMB to minimize their risk of relapse, and those who should continue AD to minimize risk of relapse) and that women who are randomized to the algorithm indicated approach will have significantly lower risk of relapse and symptom burden than women who are randomized to their algorithm contraindicated approach.

Analysis for Specific Aim #3: To test the extent to which digital MMB engages putative targets.

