If a participant scores greater than or equal to 15 on the PHQ-9 or greater than or equal to 12 on the EPDS, the online data collection and management system (REDCap) will automatically provide participants with contact information for national mental health crisis resources and for the research study team. Study investigators will be notified immediately via an algorithm programmed into REDCap. In the UPWARD parent trial and UPWARD-S Arms 1a and 2, study staff at MGH will initiate a clinical response by phone call to assess clinical status and suicidality as soon as possible within 24 business hours of report. The score of 15 is suggested as the threshold for moderate depression.³⁹ Additionally, we will monitor specifically responses to the suicide item (#9) on the PHQ-9: 'Thoughts that you would be better off dead or hurting yourself in some way.' and the suicide item (#10) on the EPDS: 'The thought of harming myself has occurred to me' for all study participants. If a participant endorses either of these items with a score of 1 or greater, REDCap will automatically route participants to fill out the Columbia Suicide Severity Rating Scale (CS-S) and provide participants with contact information for national mental health crisis resources and for the research study team. Study investigators and staff will be automatically notified by the REDCap system for a positive score on questions 3-5 of the CS-S in order to provide outreach as soon as possible within 24 hours and assessment of the patient by a study doctor. In UPWARD-S, endorsement of current suicidal ideation on the SITBI or CCM item (#11) will also automatically route participants to fill out the CS-S. Any endorsement of items 1-5 of the CS-S will prompt administration of the full CS-S to capture duration and intensity of suicidal ideation and/or behaviors. Furthermore, any participant who misses a scheduled assessment point will be contacted immediately by study staff. Study staff will continue to try to reach participants until a participant indicates that they no longer wish to be contacted or the participant has reached six months postpartum by their estimated date of delivery, whichever comes first. Throughout the study, all participants also will be encouraged to contact the study staff at the first sign of increased depression.

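### Fine-Gray with attrition as the competing event does not correct dependent censoring of relapse, and a dropout gap between arms would by itself move the relapse hazard ratio

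*Combined protocol and SAP*

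**What the plan says.** Section VI (Biostatistical Analysis), Analysis for Specific Aim #1, takes time to MINI-rated relapse through six months postpartum as the relapse outcome. It begins: "Survival rates will be compared using Cox proportional hazard regression and illustrated in Kaplan-Meier curves". It continues: "However, time to attrition is a competing risk that can be related to time to relapse". It then adopts the "subdistribution hazard model (SHM) developed by Fine and Gray to account for the possible non-independence of the censoring mechanism". It does not say whether this replaces the Cox comparison or stands beside it.

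The next paragraph, on continuous outcomes (PHQ-9, hierarchical linear models), adds pattern-mixture models that "will be used to assess whether important estimates (i.e., intervention effects) are dependent on missing data". Nothing comparable appears in the relapse paragraph.

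For H2a the section says: "Our analysis will be the same as H1 with both the time-to relapse and continuous outcome models".

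The ways of leaving the study include, under the UPWARD drop criteria in Section III, "Inability or unwillingness to complete study procedures", and also miscarriage or termination. Section VII says of missed assessments: "Study staff will continue to try to reach participants until a participant indicates that they no longer wish to be contacted".

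**The concern.** A competing event is one after which the event of interest can no longer happen. A woman who withdraws, or who stops answering, can still relapse; the trial just does not see it. Under the stated intent-to-treat population that is a missing outcome.

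Fine-Gray keeps such a woman in the risk set, relapse-free, to the end of follow-up. It uses no information on her risk after she leaves, so it cannot adjust for dropout being related to relapse. It changes the target from relapse to relapse observed before dropout. The arm that loses more women then shows fewer relapses for that reason alone.

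The most natural reading is that Fine-Gray supersedes Cox, which would make it the relapse test for H1 and, by reference, for H2a. If MMB lost more women, the analysis would lean towards a false benefit. If UC lost more, it would hide part of a real one.

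**Working it through.** **Plan's own figure.** None is given for the effect of dropout on the hazard ratio. The nearest is 95.5% power for a 20% difference in relapse with N = 600 and 30% attrition. With 0.7 × 300 = 210 per arm, a 20-point difference has at least 98.1% power at every control rate from 22% to 80%, so 95.5% is not reproduced. With 175 per arm (0.7 × 250, the number printed for the continuous outcome), continuity-corrected power is 95.6–96.3% for control rates of 50–70%. That mismatch is a separate matter and does not bear on this point.

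**Inputs from the documents.**
- Follow-up of about 12 months (Section VII).
- Overall attrition of 30% (Section VI, power for Aim 1).
- Relapse of 19% on MBCT, and 66% after stopping antidepressants (power for H2a).
- About 30% lower relapse on MBCT than on UC (power for Aim 1). Read as points, 19 + 30 = 49% on UC.
- Two-sided 0.05. Sidedness is stated for the continuous outcome only and is assumed for relapse.
- Number per arm: Section V (UPWARD Extension) gives the final 100 of the 600 women no follow-up interviews or relapse calls, and Sections V (Prospective Follow-up) and VII repeat the restriction on interviews. So (600 − 100)/2 = 250 per arm can supply MINI relapse. The Extension's schedule table still lists the MINI mood module at follow-up; I follow the text.
- H2a: half of each arm is expected to stop antidepressants, so about 125 per arm.

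**Assumptions.** Exponential relapse and dropout. *Dropout* means the chance of leaving by month 12 if no relapse occurred first. Per-arm dropout is assumed, averaging 30%.

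**Closed form.** With l = −ln(1 − relapse)/12 and m = −ln(1 − dropout)/12, relapse observed before dropout is l/(l + m) × [1 − exp(−12(l + m))]. True relapse is 49% in both arms, so 12l = 0.673.
- UC dropout 25%: 12m = 0.288, giving 0.673/0.961 × (1 − 0.51 × 0.75) = 43.3%.
- MMB dropout 35%: 12m = 0.431, giving 0.673/1.104 × (1 − 0.51 × 0.65) = 40.8%.
- At 20/40 the same steps give 44.5% and 39.5%.

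The ratio of cumulative subdistribution hazards at month 12 is ln(1 − 0.408)/ln(1 − 0.433) = 0.92 at 25/35 and ln(1 − 0.395)/ln(1 − 0.445) = 0.85 at 20/40. The ratio starts at 1 and falls with time, so a fitted SHR lies between 1 and these values.

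**Simulation.** Because all other censoring falls at month 12, Fine-Gray equals a Cox fit with dropouts kept in the risk set to month 12. A repeat run of 5,000 trials per scenario agreed with the figures below to within about 1.5 points.

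No effect, dropout independent of relapse, 250 per arm, 49% relapse in both arms:

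| Dropout UC/MMB | SHR | Fine-Gray rejects | Cox, censored at dropout |
|---|---|---|---|
| 30/30 | 1.00 | about 5% | about 5% |
| 27.5/32.5 | 0.96 | 5.8% | about 5% |
| 25/35 | 0.93 | 7.5% (7.0% favouring MMB; nominal 2.5%) | about 5% |
| 20/40 (stress case) | 0.87 | about 17% | about 5% |

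H2a, 125 per arm, 66% relapse, no effect: Fine-Gray rejects about 7% at 25/35 and 14% at 20/40.

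UC losing more (35/25), 250 per arm, UC relapse 49%, power for Fine-Gray v Cox:
- 20-point effect: 96% v 99%.
- 15-point effect: 75% v 89%.
- 10-point effect: 34% v 56%.

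**Dropout related to relapse, no effect** (true hazard ratio about 1; the strength of the link is assumed):

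| Scenario (UC/MMB dropout) | Cox | Fine-Gray |
|---|---|---|
| Shared frailty, 25/35 | 0.96 | 0.90 |
| Shared frailty, 20/40 | 0.94 | 0.83 |
| Marker triples relapse, and dropout in MMB only, 30/30 | 0.96 | 0.97 |
| Same marker, 32.5/27.5 | 0.96 | 1.00 |
| Negative dependence, 20/40 | 1.07 | 0.90 |

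Neither model is reliably nearer the truth. Where Fine-Gray lands on it, two errors have offset each other by chance.

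**The case against.** Several points on the other side stand.

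- **The gap is assumed.** No passage gives attrition by arm. The 15% and roughly 40% in the power section come from two previous studies, not from two arms. For MMB the protocol says: "Participants are asked to logon to the program on a daily basis until program completion". But that concerns use of the programme, and Section VII separates leaving the study from leaving MMB. Assessment calls and outreach apply to both arms. A reader might infer that the relapse result will be biased towards MMB; the documents do not support that. A gap is possible in either direction, and with equal dropout unrelated to relapse there is no bias under the null.
- **Cox is also named.** If both models are reported, readers will see the Cox result. A reader might take it as stated that Fine-Gray is primary; that is only the natural reading.
- **Cox is not a remedy in itself.** One might infer that Cox is always the less biased choice. The dependent-dropout scenarios do not bear that out.
- **Not all attrition is alike.** After miscarriage or termination, the planned pregnancy and postpartum endpoint is no longer straightforwardly the same. Treating that part alone as a competing event is defensible.
- **At the planned 20-point effect little power is lost** (96% v 99%).

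None of this rescues the stated purpose. Ordinary withdrawal does not preclude relapse, and Fine-Gray does not adjust for its link with relapse.

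**Conclusion.** The point holds as a fault of method, and the relapse paragraph should be corrected before analysis. Fine-Gray cannot serve the purpose the plan gives it, no other safeguard is stated for relapse, and the primary relapse model for H1 and H2a is left unnamed.

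Confidence is high on the method and lower on the practical size. A 5-point gap hardly matters, a 10-point gap raises false positives to about one and a half times nominal, and the 20-point gap is a stress case. These figures rest on exponential times, 12 months of follow-up, 49% relapse (66% for H2a), 250 or 125 women per arm, and dropout averaging 30%. The SHRs hardly change for relapse between 30% and 66%; the rejection rates depend on the number of events.

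**What to change.** In Section VI, Analysis for Specific Aim #1:

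- (a) Define withdrawal and loss to follow-up as censoring, not a competing event, and delete the statement that Fine-Gray accounts for dependent censoring.
- (b) Name one primary relapse model for H1 and H2a, for example Cox censored at the last contact that could have revealed a relapse.
- (c) State separately how pregnancy loss enters the model.
- (d) Add a dependent-censoring sensitivity analysis for relapse: inverse-probability-of-censoring weights built from the PHQ-9 and EPDS already collected, a tipping-point analysis by arm, or both. The tipping-point analysis does not rely on a measured predictor of dropout.
- (e) Report attrition by arm and by reason, with pregnancy loss and protocol-mandated removals shown separately.

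The cost is SAP wording and modest programming, with no new visits or data; dropout rates already go to the DSMB (Section IX). The weights need a stated dropout model, correct only for what the measured scores capture, and may widen intervals.

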Our understanding of community provider knowledge and skill in managing suicidal ideation and behavior among pregnant women is limited. Many women who screen positive for significant depressive symptoms during pregnancy fail to be referred for treatment and among those who receive treatment, the interventions received are not associated with restoration of euthymia.²¹ Within the general population, qualitative methods have been informative in understanding models of care,²³ provider training on suicide and self-harm risk assessment,²⁴ policies for supporting patients at risk for suicide,²⁴ referral processes,²³ interventions for suicide prevention,²³ access to mental health providers within the health setting,²⁵ perceptions regarding the importance of patient access to a mental health provider for comprehensive care,²⁵ barriers and challenges to providing patients with care,²³ support available for providers following the death of a patient by suicide,²⁴ and personal experiences with mental health.²⁵ It is critical to understand the knowledge and resources in community settings that care for perinatal women to inform future health service and provider education efforts.

II. SPECIFIC AIMS

UPWARD Study

Objective: The overarching objective of this investigation is to conduct a pragmatic effectiveness trial comparing Mindful Mood Balance for Moms (MMB), a digital MBCT program, plus UC to UC only among euthymic pregnant women with recurrent depression treated with AD.

Aim 1: To test the relative risk for depressive relapse and reduction of symptom burden between women randomized to digital MMB or UC.

Hypothesis 1: We predict that relative risk for depressive relapse and reduction of symptom burden will be significantly lower among women randomized to digital MMB relative to women randomized to UC.

Aim 2: To explore the specific benefit of MMB relative to AD discontinuation and questions regarding personalization that are of strong interest to pregnant women and their healthcare providers.

Hypothesis 2a. We predict that relapse risk and symptom burden among women who discontinue AD will be significantly lower among those randomized to MMB than UC.

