In UPWARD, UPWARD Extension and UPWARD-S, if suicidality is endorsed with a score of greater than 1 on EPDS item #10 or PHQ-9 item #9 or on any of the self-report questionnaires (such as the SITBI or CCM), subjects will be prompted to complete the CS-S to assess risk of suicidality. Study subjects will also be given the national suicide [contact]) and informed that answers to online questionnaires are not monitored in real time. A positive score on questions 3, 4, or 5 on the CS-S, indicating intention or plan for suicidality, will prompt a safety call by study physicians. Suicidality expressed during the course of clinical or qualitative interviews, either through discussion, endorsement of the suicidality item on the MINI mood module, endorsement of items 3, 4, or 5 on the suicidality module of the MINI, or via scoring >2 on the MADRS item 10, will prompt study staff to complete the CS-S with the participant. A positive score on items 3, 4, or 5 of the CS-S administered by staff will also prompt a safety call by study physicians. In addition, subjects will be told by study staff to call their community providers and go to their nearest emergency room. Endorsement of items 3-5 on the CS-S prompting a physician safety call has been the threshold used in previous studies at the collaborating site (University of Colorado Boulder). As this is a community-based study with collaboration from community physicians, these providers dictate treatment. We will notify community providers directly via phone or fax within 24 hours from report of positive scores on CS-S items 3-5.

VI. BIOSTATISTICAL ANALYSIS

Preliminary Analyses: Differences between the MMB and UC in demographic characteristics and depression related characteristics (e.g., symptom severity, comorbidity) will be assessed using Chi-square test for binary variables, Cochran Mantel Haenszel tests for categorical variables, and t-tests for continuous variables. Variables that show significant group differences and predict outcome will be entered in analyses as covariates; AD exposure will be included as a covariate. All participants will be considered evaluable for analysis (intent-to-treat sample). Significance levels will be evaluated at $p < .05$, and effect sizes reported.

Analysis for Specific Aim #1: To test the relative risk for depressive relapse and reduction of symptom burden between women randomized to digital MMB or UC.

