To test target engagement, we will use the same HLM methods described above to compare differences between MMB and UC in change in the putative targets during the intervention period. To test target validation, we will use recent statistical developments that apply formal causal inference concepts to mediation analyses. Causal mediation approaches address violations of the assumption of sequential ignorability (e.g., no confounding/randomization of the mediator) that is required for unbiased estimates of the M (mediator) \rightarrow Y (outcome) relationship. Addressing the issue of sequential ignorability yields unbiased estimates of the natural direct effect (NDE = the non-mediated effect of reduction of depressive related outcomes) and the natural indirect effect (NIE = the component of the intervention that seems to proceed through the respective mechanisms), with Total Effect = NDE + NIE.²⁷ A high NIE indicates that the subsequent outcomes are mediated through time-lagged mechanisms improvements. We have experience implementing these models which fall under the classification of marginal structural models (MSM), principal stratification (PS), structural nested mean models (SNMM), and rank preserving models (RPM),²⁸⁻³⁰ which we will apply for each putative target individually. Sensitivity analyses will be implemented using approaches outlined by Ding and VanderWeele.³¹

Power Analysis for Specific Aim #1: To test the relative risk for depressive relapse and reduction of symptom burden between women randomized to digital MMB or UC.

For the analysis of rates of relapse, in our efficacy study of MBCT,³² pregnant women who received MBCT evidenced approximately 30% lower rate of relapse than UC. In estimating the difference in relapse rates between MMB and UC, accommodating the sample size required to address Aim 2, N = 600 participants is required for randomization. With N=600, we have 95.5% power to detect a 20% difference in relapse rates (which is smaller than what we observed in our efficacy study) and allowing for 30% attrition, which is higher than attrition in our efficacy study of MBCT with pregnant women (15%) and lower than attrition in our digital delivery of MBCT work (approximately 40%).

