For the continuous outcomes, using the method described by Ahn et al. to derive formulas for power estimation of linear mixed models,³³ power calculations can be made for repeated measures designs under specified assumptions. Based on a sample size of 300 per group, assuming 30% attrition for a total of 175 per arm randomized, with an alpha-level at 0.05 based on a 2-tailed test, assuming a within correlation of 0.5, we have power of 86.5% to detect an effect size of .25. Varying the effect size, we have 95.7%, 99.0%, and 99.8% power for effect sizes of 0.3, 0.35, and 0.4 respectively, which are much smaller than the d=0.70 effect size

observed in our efficacy study of MBCT with pregnant women,³⁴ indicating that we are sufficiently powered.

Power Analysis for Specific Aim #2: To explore the specific benefit of MMB relative to AD discontinuation and questions regarding personalization that are of strong interest to pregnant women and their healthcare providers.

H2a: Comparison of MMB to UC among women who discontinue AD: Anticipating balance across the 4 cells (randomized to MMB or UC; choice of discontinue AD or maintain AD), with approximately 300 participants across the two cells of interest, we have 82.8% power to detect a 23% difference in relapse rates with 30% attrition, which is smaller than what would be expected comparing the relapse rates among women who received MBCT (19%) in the [name] et al. study of MBCT with pregnant women³² to the rate of relapse among women who discontinued AD during pregnancy (66%) in the Cohen et al. prospective study¹⁰).

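### The primary PHQ-9 model does not name the contrast that decides it: time shape, coefficient, window and use of baseline are all left open

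*Combined protocol and SAP*

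**What the plan says.** Section VI, Analysis for Specific Aim #1, makes a hierarchical linear model (HLM) the primary model for continuous outcomes, "which will compare change over time between groups on depressive symptom burden using the PHQ-9". The next sentence leaves the time function open: "HLM is flexible with respect to the nature of change over time (i.e., linear, piecewise linear, loglinear, etc". Nothing in the document picks a shape, a knot, a time window, the parameter to be tested, or a rule for choosing among shapes.

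The hypotheses in section II do not settle it. Hypothesis 2a concerns a level: "We predict that relapse risk and symptom burden among women who discontinue AD will be significantly lower among those randomized to MMB than UC". Hypothesis 1 is worded differently: "relative risk for depressive relapse and reduction of symptom burden will be significantly lower among women randomized to digital MMB". Read literally, that predicts a smaller reduction with MMB; it looks like a slip of wording, and nothing below rests on it.

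The Preliminary Analyses paragraph states "Significance levels will be evaluated at $p < .05$, and effect sizes reported", with no multiplicity rule. It admits baseline variables as covariates only if they differ significantly between groups and predict outcome. So baseline PHQ-9 would enter as a covariate only if it happened to be imbalanced.

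The power paragraph says "we have power of 86.5% to detect an effect size of .25", without naming the contrast or the number of visits.

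**The concern.** A group difference in linear slope, in loglinear slope, in the first or second segment of a piecewise line, and in mean level over follow-up are five different tests. They can disagree on the same data. Without a named contrast or a selection rule fixed in advance, a positive or null PHQ-9 result may reflect the chosen shape.

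The choice also affects whether the test measures what is hypothesised. Women enter with PHQ-9 of 9 or less, the intervention lasts 12 weeks, and participation runs about 12 months. A gap that opens during the intervention and then holds is one plausible form of benefit, and a straight line over the whole period captures it only in part. A gap that widens postpartum is also plausible, and there the slope does well. The analysis of H2a reuses the Aim 1 models, so it inherits the gap.

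**Working it through.** **Inputs.** From the power analysis for Aim 1: 175 per arm, within-subject correlation 0.5, effect size 0.25, "with an alpha-level at 0.05 based on a 2-tailed test". (Thirty per cent attrition from 300 leaves 210, not 175; that is a separate matter.) Assumed here: unit variance; scheduled PHQ-9 visits mapped from Table 1 to months 0, 1, 1.5, 2, 3, 4, 5, 5.5, 6, 7, 8, 9, 10, 11, 12, 12.5; two-weekly PHQ-9s left out; no dropout beyond the reduced n. Power = Φ(effect/SE − 1.96), plus the opposite tail where it matters.

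**Step 1: does the stated power reveal the contrast?**
- Mean of 6 visits, 175 per arm: variance (1 + 5×0.5)/6 = 0.583; SE = √(2/175 × 0.583) = 0.0816; 0.25/0.0816 = 3.06; power 86.5%.
- Linear slope over 8 equally spaced visits, effect taken as the end difference: 0.5/0.857 = 0.583, hence the same SE and the same 86.5%.
- One measurement, 300 per arm, no attrition: 2/300 = 2/175 × 0.583, again 86.5%.

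Each version also gives 95.7%, 99.0% and 99.8% for 0.30, 0.35 and 0.40. The stated figures reproduce exactly but do not show which test was meant.

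**Step 2: false positives if any significant term is claimed.** Each group-by-time coefficient is a weighted sum of the data, so the z statistics are jointly normal, with correlations fixed by the weights. Simulating P(any |z| > 1.96) under three assumed covariances (compound symmetry; random intercept and slope; serial correlation):
- linear or loglinear: 6.5–7%;
- linear, loglinear or a joint 2-df piecewise test: 8.5–9.0%;
- any of linear, loglinear and two piecewise slopes: about 13% (four independent tests would give 1 − 0.95⁴ = 18.5%).

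**Step 3: power by contrast under compound symmetry, correlation 0.5.** Σt = 97.5, Σt² = 838.75. Let y be the group difference at each visit.

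Sustained benefit (rises to 0.25 at month 3, then flat): Σy = 3.375, Σty = 23.854.
- Slope, separate group intercepts: (23.854 − 97.5×3.375/16)/(838.75 − 97.5²/16) = 3.288/244.61 = 0.01344; SE = √(2/175 × 0.5/244.61) = 0.00483; z = 2.78; power 79%.
- Slope, common baseline across arms (16 becomes 17 in both corrections): 4.498/279.56 = 0.01609; SE 0.00452; z = 3.56; power 94.5%.
- Follow-up mean: effect 3.375/15 = 0.225; variance (1 + 14×0.5)/15 = 0.533; SE 0.0781; z = 2.88; power 82%.
- Follow-up mean, baseline-adjusted: variance 0.533 − 0.5² = 0.283; SE 0.0569; z = 3.95; power 98%.

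Linear growth to 0.25 at the end (0.02 per month): common-baseline slope z = 0.02/0.00452 = 4.42, 99%; adjusted mean 0.02×97.5/15 = 0.13, z = 2.28, 63%.

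Benefit halving between month 3 and the end: Σy = 2.625, Σty = 16.584. Common-baseline slope 1.529/279.56 = 0.00547, z = 1.21, 23%; adjusted mean 2.625/15 = 0.175, z = 3.08, 87%.

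**Step 4: ranges over the three assumed covariances, 175 per arm.**

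| Benefit | Slope, baseline not used | Slope, common baseline | Follow-up mean, baseline-adjusted |
|---|---|---|---|
| Sustained from month 3 | 44–79% | 77–95% | 95–98% |
| Linear growth to the end | 54–98% | 76–99% | 54–63% |

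For sustained benefit, with baseline used, the loglinear slope and the first piecewise slope (knot at month 3) have 86–99%.

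**The case against.** The plan fixes the outcome, the scale and the model class. Choosing a time function by fit is ordinary HLM practice, and the shapes it lists include two that suit a gap which opens early and holds. All of that stands. It does not close the gap: no selection rule is given, and even a best-fitting piecewise model leaves two slopes with no statement of which one decides.

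Three stronger readings are tempting, and the documents do not support them.
- A reader might infer a 13% error rate. The plan nowhere says that four coefficients will be tested and any of them claimed, or that the shape will be chosen after seeing results by arm.
- A reader might infer that the trial will miss a sustained benefit because slopes are weak. The plan does not commit to a straight line. Much of the shortfall against an adjusted mean comes from baseline use: under compound symmetry the slope and mean are 79% and 82% without baseline, and 94.5% and 98% with it.
- A reader might extend the point to Aim 3, where "we will use the same HLM methods described above to compare differences between MMB and UC in change in the putative targets". That comparison is already limited to the intervention period, so the 12-month slope argument does not carry over.

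The averaged contrast is also a trade-off rather than a clear winner: it loses substantially if benefit grows steadily to 6 months postpartum.

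**Conclusion.** The concern holds as a gap in specification. The primary continuous analysis has no named deciding contrast, and both the error rate and the power depend on what fills that gap. The illustrative false-positive rates of 6.5–7% and about 13% rest on an assumed claim-any-term rule. The power ranges rest on the assumed visit mapping, benefit patterns and covariances; only the 0.5 correlation, 175 per arm and 0.25 effect come from the plan, so the ends of the ranges are not bounds. Two conclusions do not depend on which pattern is true. One pre-specified contrast holds the error rate at 5%, and for a given contrast, using baseline PHQ-9 raised or kept power in every pattern tried. Which contrast has most power does depend on the pattern.

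**What to change.** In the Aim 1 analysis text, before any unblinded analysis:
1. Name one deciding PHQ-9 contrast that uses baseline PHQ-9, either as a covariate or through a common baseline across arms, whether or not baseline is imbalanced. A suitable choice is the baseline-adjusted MMB-minus-UC difference averaged over scheduled post-baseline visits, with time as categories in the same HLM, because it matches symptom burden as hypothesised. If the sponsor expects benefit to build gradually, a common-baseline slope is defensible; what matters is that one is fixed.
2. State the window and how the final 100 participants (UPWARD Extension), followed only to 3 months postpartum, enter it. A window to 6 months postpartum rests its last visits on the first 500 women, whose MMB included coaching; one to 3 months postpartum covers all 600 but drops later follow-up.
3. Declare the other trajectory shapes descriptive, with no significance claim.
4. Use the same contrast for H2a, and say in the power paragraph which contrast the 0.25 refers to.

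No change is needed for Aim 3. The cost is wording only, with no new data, visits or participants. The price of the averaged contrast is lower power under gradual benefit: 63% against 99% for the common-baseline slope under compound symmetry.
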